6.2 Preparation/Handling/Storage/Accountability

6.2.1 *Acquisition and accountability*

The **M3** and **M4** vaccines will be manufactured and provided by IDT Biologika, Germany. Study products will be provided directly to the UNC Investigational Drug Services (IDS), and dispensed and administered according to site and study-specific SOPs.

Both investigational products will be used as supplied by the manufacturer.

The study site will supply the normal saline used for the placebo injections.

The primary IDS pharmacist will be responsible to the Principal Investigator (PI) for maintaining study drug accountability, reconciliation, preparation, distribution, and record maintenance during the study, including documentation of the amount of both study treatments (**M3** and **M4**) received in IDS and the amount administered to each participant.

The cleanup and disposal of spilled, wasted, or unused medication and used syringes must be documented appropriately (i.e., witnessed) in accordance with applicable federal regulations, Good Clinical Practice (GCP) procedures, and the procedures for handling biohazardous substances. Any incidents related to **M3** and **M4** vaccines and employee/participant exposure or employee needle sticks must be reported immediately to the UNC Institutional Biosafety Committee (IBC) and NIH Office of Science Policy (OSP) as per the NIH Guidelines for Research Involving Recombinant or Synthetic Nucleic Acid Molecules dated April 2016.

An accountability form and dispensing log, documenting vial allocation number and date, will be kept during the study and will be available for monitoring and inspection/auditing as required. All unused vials will be stored in a designated local freezer at the end of each vaccination visit. Any used vials and expired pre-filled syringes should be disposed of in accordance with institutional or pharmacy policy.

6.2.2 *Formulation, Appearance, Packaging, and Labeling*

MVA.tHIVconsV3 (M3) vaccine is a white cloudy solution, formulated in Tris-saline buffer (10 mM Tris HCl, 140 mM NaCl, pH 7.7) at a concentration of 3.4×10^8 pfu/ml. The extractable fill volume is 500 μ l. The product is supplied in sterile rubber-stopped glass vials.

MVA.tHIVconsV4 (M4) vaccine is a white cloudy solution, formulated in Tris-saline buffer (10 mM Tris HCl, 140 mM NaCl, pH 7.7) at a concentration of 1.8×10^8 pfu/ml. The extractable fill volume is 500 μ l. The product is supplied in sterile rubber-stopped glass vials.

M3 and M4 vaccines will be packaged and labeled at the manufacturing facilities.

The vaccines will be labelled or have accompanying documentation indicating compliance with GMP and other regulatory requirements. The minimum information provided by the manufacturer includes:

- Study product name and concentration
- Manufacturer
- Date of manufacture
- Lot number
- Volume
- Expiration date (or re-test date)

Investigational vaccine release will comply with procedures required by International Council for Harmonization of Technical Requirements for Pharmaceuticals for Human Use Good Clinical Practice (ICH)-GCP. The study PI provides written authorization for the shipment of the **M3** and **M4** vaccines to UNC after confirmation that all critical documents required for shipment authorization are completed. The investigational vaccines are shipped to UNC in cryoshippers with temperature monitoring capacity.

6.2.3 Product Storage and Stability

M3 and M4

The **M3** and **M4** vaccines are stored frozen at $\leq -65^{\circ}\text{C}$ (nominal temperature) in a locked freezer at IDT Biologika according to good manufacturing practice (GMP). Upon QP certification to trial and associated labelling to trial, the vaccine will be transferred to the UNC IDS.

Once received in the IDS at UNC, the study vaccines are transferred to temperature-monitored storage at $\leq -65^{\circ}\text{C}$ in a locked freezer (IB, MVA.tHIVconsV3 version 2.0; IB, MVA.tHIVconsV4 version 2.0). The freezers must be temperature monitored and if temperature goes outside the normal range, appropriate action is required in accordance with previously agreed SOPs. The placebo (normal saline) will be stored at room temperature.

A vaccine accountability log will be used to record the removal, including the time of removal, and use of each vaccine vial. Vaccine accountability, storage, shipment, and handling will be in accordance with the relevant IDS SOPs and forms.

Preparation

Dispensing and Handling

UNC IDS will prepare and dispense all study product according to UNC and/or study-specific SOPs.

M3 and M4 vaccines and placebo will be dispensed from the UNC IDS Pharmacy, where only the pharmacist(s) will be un-blinded.

Following randomization in IDS, the designated vaccine product(s) will be thawed, without shaking, until completely liquid by holding the vial in a gloved hand.

The vials will not be shaken.

All syringes (vaccine and placebo) will be covered with opaque tape and a label in the UNC IDS Pharmacy to maintain blinding.

Arm 1 - Using aseptic technique, withdraw the needed volume of M3 from the vial into a syringe. Affix a needle suitable for IM injection for administration.

Arm 2 - Using aseptic technique, withdraw the needed volume of M4 from the vial into a syringe. Affix a needle suitable for IM injection for administration.

Arm 3 - Using aseptic technique, withdraw the needed volume of M3 and M4 from each vial into a single syringe. Affix a needle suitable for IM injection for administration.

Arm 4 - Using aseptic technique, for placebo draw the appropriate amount of Sodium Chloride for Injection USP, 0.9% into a syringe. Affix a needle suitable for IM injection for administration.

Following study product preparation, all vaccine/placebo study product should be kept at room temperature until administered. Vaccines must be administered within 60 minutes (1 hour) of removal from the freezer.

Any unused portion of entered vials and expired pre-filled syringes should be disposed of in accordance with institutional or pharmacy policy.

6.3 Measures to Minimize Bias: Randomization and Blinding

Randomization

The 24 study participants will be randomly assigned to receive one vaccination with **M3** (n=7) or **M4** (n= 7) or **M3 + M4** (n=7) or placebo (n=3) through a blinded randomization schedule. When the participant's eligibility is confirmed, the study specific identification numbers (SIDs) will be assigned sequentially as each participant enrolls at the study at the Enrollment Visit. Vaccine and placebo product will be indistinguishable. Site and laboratory personnel and participants will be blinded with respect to the allocation of

vaccine or placebo. A double-blind placebo-controlled design has been chosen to minimize bias in the reporting of safety and immunological data.

Participants will be randomized and assigned an RID on Day 0 in the IDS pharmacy after receipt of vaccine/placebo prescription. The randomization plan will be generated centrally by the study statisticians at the UNC CFAR using computer software, and will be kept concealed from study personnel.

Un-blinding

Un-blinding of an individual participant is indicated in the event of a medical emergency where the clinical management would be altered by knowledge of the group assignment. The decision to un-blind will be taken in conjunction with the independent members of the Study Monitoring Committee (SMC). Procedures and contact details for un-blinding procedures will be specified in a site-specific SOP. The site personnel will ensure that the reasons for un-blinding are documented in the clinical research chart.

6.4 Study Intervention Compliance

Participants will keep a daily diary of solicited AEs for both local and systemic symptoms for 3 days after the vaccine/placebo administration.

6.5 Concomitant Medications

Whenever a concomitant medication is initiated or the dose is changed for all participants after receipt of vaccine/placebo at Day 0 through Day 28 of the study, the PI (or designees) must review the concomitant medications' most recent package inserts, investigator's brochures, or updated information from DAIDS to obtain the most current information on drug interactions, contraindications, and precautions.

Required Medications

1. All participants will be required to have durable HIV suppression on ART for ≥ 24 months prior to study screening and maintain ART therapy throughout the entire study. The study will not provide ART medications.

The study team will consider alternate ART regimens on a case-by-case basis prior to enrollment per eligibility criteria. The study permits the use of all approved PIs, NNRTIs, NRTIs, and fusion and integrase inhibitors. Also permitted are changes to the participants' ART during the study for dosing simplification, tolerability issues, and improved side effect profile or at the investigator's discretion. If a participant develops toxicity related to his/her previously stable ART, consult the protocol team (preferably before appropriate therapy modification).

Prohibited Medications

1. Ongoing use of investigational ART with the exception of Phase II studies of antiretroviral therapy.
2. Concomitant use with oral or parenteral corticosteroids, immunosuppressive agents (including but not limited to chronic topical steroids or steroid containing inhalers, azathioprine, and cyclosporine) or any immunotherapy or immunomodulatory agents;
3. Antihistamine from 7 days prior to vaccination through Day 14;
4. Standard vaccines (e.g., pneumococcal, Hepatitis A, Hepatitis B) and live vaccinations (e.g., varicella, measles, mumps, rubella, MMR; yellow fever, oral polio) except influenza and COVID-19 are prohibited from 28 days prior to screening through Day 28 (reference Sections 5.1 and 5.2);
5. Any agent that suppresses lymphocytes or monocyte function;
6. Chemotherapeutic agents, growth factors, cytokines, or chemokines, white lineage colony stimulating factors (e.g., granulocyte-colony stimulating factor [G-CSF] and GM-CSF);
7. Chronic use of topical corticosteroids applied to large areas of the skin (exceeding the cumulative area of the palm of the participant's hand);
8. Sporadic topical use of corticosteroids (e.g. creams) to small areas of the skin (<15 cm²) for participants who are receiving ritonavir or cobicistat as part of their current ART regimen;
9. Any form of corticosteroid or antihistamine medications at or near the injection site, including for treatment of injection site reactions;
10. Refer to exclusion criteria in [Section 5.2](#).

Rescue Medicine

Not applicable.

7 STUDY INTERVENTION DISCONTINUATION AND PARTICIPANT DISCONTINUATION/WITHDRAWAL

7.1 Discontinuation of Study Intervention

Premature Treatment Discontinuation Evaluations

There is only one study treatment intervention visit at Day 0. The collection of safety labs, virologic, immunologic, SCA, and the 2nd leukapheresis will continue to be collected per SOE, section 1.3.

Participants who complete the vaccine/placebo injection but do not complete the Day 7 study visit will be replaced, provided the inability to complete the Day 7 visit is not due to a study-related AE.

Participants who complete the vaccine/placebo injection but do not complete the Day 28 study visit and 2nd leukapheresis procedure will be replaced, provided the inability to complete the Day 28 visit is not due to a study-related AE.

Participants who receive vaccine/placebo but are unable to complete the Day 7 or 2nd leukapheresis should be encouraged to continue on study for safety assessments per the SOE.

Discontinuation of Antiretroviral Therapy

If the participant discontinues ART prior to DAY 0, DO NOT give the vaccine/placebo injection. DO NOT collect research labs for the time points after the participant discontinued ART. This participant will be replaced.

If the participant discontinues ART after the vaccine or placebo administration (Day 0), the participant should continue on study for safety follow-up as noted in the SOE. Collection of virologic, immunologic, SCA, and the 2nd leukapheresis samples will be determined on a case-by-case basis in discussion with the protocol team. This participant may be replaced.

7.2 Participant Discontinuation/Withdrawal from the Study

1. Enrolled Participants, who are not Randomized and Do Not Start Study Treatment
 - a. Participants who withdraw or who are withdrawn from the study after the Enrollment Visit but prior to receipt of vaccine/placebo:
 - DO NOT re-use the SID.
 - REPLACE the participant.
 - b. A participant who is unable to complete the leukapheresis procedure or from whom < 40 ml is collected prior to Day 0 will be terminated from the study.
 - DO NOT re-use the SID.
 - REPLACE the participant.
 - Termination can occur due to complications at the leukapheresis procedure as determined by the Clinical PI (or designee) and the Apheresis Medical Director and can include contraindications for further leukapheresis procedures.

- c. Participants who complete the first leukapheresis procedure pre-vaccine but do not want to do the second leukapheresis procedure will be withdrawn from the study.
 - DO NOT re-use the SID.
 - REPLACE the participant.
2. Evaluations for Randomized Participants Who Do Not Start Study Treatment
 - a. Participants who withdraw or are withdrawn after randomization but prior to starting study treatment (vaccine or placebo) will have no further evaluations or follow-up.
 - Notify IDS of the withdrawal and the randomization assignment.
 - RE-ASSIGN the Randomization Identification (RID).
 - DO NOT re-use the SID.
 - REPLACE the participant.
3. Evaluations for Randomized Participants Who Received Study Product and are Discontinued or Withdrawn from Study Participation.
 - a. Participants who withdraw or are withdrawn after randomization and prior to Day 28, will have no further research evaluations or follow-up (based on review by PIs) but will be encouraged to complete EOS safety evaluation visit.
 - Notify IDS of the withdrawal and the randomization assignment.
 - REASSIGN the RID.
 - DO NOT re-use the SID.
4. A participant may withdraw or be withdrawn from the study if any of the following occurs:
 - Request by the participant to withdraw from the study and study procedures.
 - Development of an illness that requires treatment with medications prohibited in this study.
 - Change in the participant's medical condition that might make continuation in the study harmful to participant.
 - Participant does not continue to meet eligibility requirements.
 - Participant does not complete Day 7 research assays.
 - Request of the participant's primary care provider if she/he thinks the study is no longer in the best interest of the participant.
 - Participant judged by the study Principal Investigator (or designee) to be at significant risk of failing to comply with the provisions of the protocol, as to cause harm to self or seriously interfere with the validity of the study results.
 - At the discretion of the IRB/Ethics Committee, FDA, NIH, and other government agencies as part of their duties, Principal Investigator (designee), or vaccine supplier.

Premature Study Discontinuation (D/C) Evaluations

Participants who prematurely discontinue study participation after completing the vaccine/placebo at Day 0 but before Day 70 will have premature study discontinuation (D/C visit) evaluations performed per the SOE for Day 70. Participants who discontinue the study prior to the 2nd leukapheresis without having met the primary safety outcome measure will be replaced, provided the discontinuation from study was not due to a study-related AE.

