9.2.1.1 Procedure for accounting for missing and unused data

Based on previous experience with similar trials, we anticipate that the amount of missing or invalid data will be small. All participants who are evaluable for adverse event assessment will be included in the safety analyses, regardless of whether they are replaced or missing for additional endpoints. Participants who do not start study treatment or are unable to provide the first or second leukapheresis will be replaced to achieve the planned evaluable sample size. Given the small size of this study, formal imputation methods will not be used. To assess whether key findings are sensitive to missing data, missing values can be replaced with worst possible outcomes as a sensitivity analysis (e.g., by replacing missing values in the M3 and M4 only arms with the best rank and replacing missing values in the M3+M4 arm with the worst rank, to assess if a finding regarding the M3+M4 arm is sensitive to missing data).

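### Section 7.2 by default ends scheduled follow-up for dosed participants withdrawn before Day 28, which conflicts with Section 7.1 and with Section 7.2's own discontinuation visit and can cost primary safety data

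*Combined protocol and SAP*

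**What the plan says.** The primary endpoint (Sections 1.1 and 3) is at least one related adverse event of Grade 3 or higher, laboratory toxicities included, from the day of treatment through 28 days after vaccination. Section 9.3.3 estimates its probability as a proportion with a one-sided 95% exact upper limit.

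Four places govern a dosed participant who leaves early or misses a procedure:

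- **Section 7.2, item 3a.** Those who withdraw or are withdrawn before Day 28 "will have no further research evaluations or follow-up (based on review by PIs) but will be encouraged to complete EOS safety evaluation visit". Their randomization number is reassigned.
- **Section 7.2, item 4.** "A participant may withdraw or be withdrawn from the study if any of the following occurs". The list includes "Participant does not complete Day 7 research assays" and "Development of an illness that requires treatment with medications prohibited in this study".
- **Section 7.1.** Dosed participants "unable to complete the Day 7 or 2nd leukapheresis should be encouraged to continue on study for safety assessments per the SOE". For someone who stops antiretroviral therapy after Day 0, "the participant should continue on study for safety follow-up as noted in the SOE".
- **Section 7.2, closing paragraph on premature discontinuation.** Anyone who discontinues after dosing and before Day 70 will have a discontinuation visit with the Day 70 evaluations.

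On analysis, Section 9.2.1.1 says: "All participants who are evaluable for adverse event assessment will be included in the safety analyses", whether or not they are replaced. Section 8.3.3 records events until 7 days (non-serious) or 30 days (serious) after the last day of participation.

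**The concern.** A participant who has had the injection but misses the Day 7 research assays falls under two rules. Section 7.1 keeps that person in safety follow-up. Section 7.2 allows withdrawal and then, by default, stops scheduled follow-up inside the primary safety window. A missed research sample has no bearing on whether safety can still be observed, so nothing is gained by losing the safety data with it.

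The prohibited-medication trigger is a separate route. Section 6.5 prohibits oral and parenteral corticosteroids, antihistamines through Day 14, and either class at or near the injection site even to treat injection-site reactions. Treatment of a vaccine reaction could therefore be what prompts withdrawal, and loss by this route could be related to the outcome.

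With seven participants per arm, one incompletely observed person visibly changes the primary estimate. An unseen event also cannot count toward the two-participant safety pause in Section 10.1.6.

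**Working it through.** **1. The rules side by side**

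| Situation after dosing | Section 7.1 | Section 7.2, items 3a and 4 | Section 7.2, closing paragraph |
|---|---|---|---|
| Day 7 missed or its assays incomplete | Encourage to continue safety assessments | May be withdrawn; then no further follow-up by default, end-of-study visit encouraged | If discontinued, a visit with Day 70 evaluations will be done |
| Illness needing prohibited medication | No rule | Same as above | Same as above |
| Replacement | Not if the cause is a study-related AE | Number reassigned, no exception stated | Not if the cause is a study-related AE or the primary outcome has been met |

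The text run into the heading of Section 8.2.5 also replaces withdrawn participants without the study-related AE exception. The conflict with Section 7.1 is confined to the missed Day 7 (or second leukapheresis) case. The conflict within Section 7.2, between a visit that is encouraged and one that will be done, applies to every early exit.

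**2. What part of the window can go unobserved**

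The Schedule of Events places post-vaccine assessment, blood count and safety chemistries at Days 7, 14 and 28. Take a participant whose last day is Day 7:

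- non-serious events are recorded to Day 7 + 7 = Day 14, so Days 15 to 28 are uncovered;
- serious events are recorded to Day 7 + 30 = Day 37, which covers the window;
- the Day 14 and Day 28 laboratory tests are not scheduled.

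Non-serious recording reaches Day 28 only if exit is on Day 21 or later (21 + 7 = 28). The closing paragraph of Section 7.2 sets no date for its discontinuation visit, so how much of the window that visit covers is unknown.

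**3. Effect on the upper limit**

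For x events in n participants, the limit U solves P(X ≤ x | n, U) = 0.05. For x = 0 this is U = 1 − 0.05^(1/n).

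The plan's own per-arm figures (Section 9.2.1) reproduce:

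- 0/7: 1 − 0.05^(1/7) = 34.8% (stated 35%)
- 1/7: (1 − U)^7 + 7U(1 − U)^6 = 0.05 gives 52.1% (stated 52%)

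The stated pooled 13% matches 0/21 (13.3%), the three vaccine arms. The n = 24 printed beside it would give 11.7%.

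The number lost is an assumption, because the documents give no withdrawal rate. For one arm with no observed events:

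| Participants unobserved | Excluded | Counted as events |
|---|---|---|
| 0 | 0/7: 34.8% | – |
| 1 | 0/6: 39.3% | 1/7: 52.1% |
| 2 | 0/5: 45.1% | 2/7: 65.9% |

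If one truncated participant stays in the denominator and a replacement is added, the limit is 31.2% (0/8) when that person is taken as event-free and 47.1% (1/8) when counted as an event. The first is tighter than planned although the data are less complete.

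Pooled over the vaccine arms, exclusion moves the limit little: 13.3% (0/21), 13.9% (0/20), 14.6% (0/19). The effect is mainly on the per-arm estimates.

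**The case against.** The other side has a good deal of text behind it.

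- *Withdrawal is discretionary.* Item 4 is permissive and item 3a is subject to review by the PIs. This stands, but no criteria guide that discretion and the written default is to stop.
- *The sections can be read together,* with Section 7.1 for those who stay and item 3a for those who leave. Item 3a might also be read as ending only research follow-up. Either reading is possible, but incomplete Day 7 assays are themselves listed as a ground for leaving, and the only safety contact item 3a names is an encouraged visit.
- *A discontinuation visit will be done.* The Day 70 evaluations include a blood count and safety chemistries. This stands against any claim that follow-up simply ceases. One undated visit does not, however, replace the Day 14 and Day 28 assessments, and a transient laboratory abnormality could be missed.
- *Known related events are not dropped.* Sections 8.2.10 and 8.3.3 follow related events to resolution, and Section 8.3.5 does so for related Grade 3 and 4 events and unresolved SAEs. A reaction that prompts prohibited treatment has already come to the site's attention. Most expected reactions appear within 24 hours (Section 2.3.1), before Day 7. This largely answers the worry about the triggering event. It does not cover a new event after exit.
- *Section 9.2.1.1 keeps evaluable participants and allows a worst-outcome analysis.* It does not define evaluable for someone seen for under 28 days. The sensitivity analysis is optional, and its example concerns ranks between arms rather than the safety proportion.

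Three stronger readings are tempting and not supported. A reader might infer that withdrawn participants receive no further follow-up at all; PI review, the encouraged visit and the discontinuation visit say otherwise. A reader might infer that the prohibited-medication trigger contradicts Section 7.1; that section has no rule on it. A reader might infer that withdrawn participants are counted as event-free and then replaced; the plan states no such counting rule, and Section 7.1 and the end of Section 7.2 bar replacement when the cause is a study-related AE.

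**Conclusion.** The point holds as a conflict between stated rules that puts primary data at risk. It does not show that data will be lost. Item 3a's default can end scheduled safety assessment inside the Day 28 window, and a missed research assay is enough to permit it. Section 7.1 and the closing paragraph of Section 7.2 point the other way. Withdrawal for prohibited medication is a second route, by which loss could be related to the outcome. It is a question of informative loss and is softened by the rules on following known related events.

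The percentages in the working illustrate sensitivity and do not forecast it. They assume one or two unobserved participants in an arm with no observed events, and Section 9.2.1.1 itself expects little missing data. They do show that, at seven per arm, the choice between excluding one person and counting that person as an event separates 39.3% from 52.1%, and the plan does not make that choice.

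**What to change.** 1. Reconcile Section 7.1, Section 7.2 items 3a and 4, the closing paragraph of Section 7.2 and the replacement text at Section 8.2.5, including whether the replacement exception for study-related AEs applies throughout.
2. State that stopping research sampling, including for a missed Day 7 assay, leads to replacement for immunogenicity only and does not end safety follow-up unless consent is withdrawn.
3. Keep dosed participants, where they agree, on the scheduled AE and safety-laboratory assessments through Day 28 and on the Day 84 and Day 168 contacts. Telephone contact can be a fallback for clinical events only: it cannot detect the laboratory toxicities in the endpoint, and Section 8.2.8 describes no call at Day 14 or Day 28.
4. State how participants observed for under 28 days enter the primary proportion, and specify a sensitivity analysis that counts them as events.
5. Report Day 28 completeness of safety follow-up by arm.

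The cost is protocol wording plus a few retained visits or contacts. Section 8.1 already provides for remote visits in defined circumstances. None of this bears on which treatments a participant should be allowed.
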